5.5.1. Confidentiality

All data will be handled in accordance with the EU Data Protection Directive (95/46/EC) and applicable national requirements. The CRFs will not contain the subject's name or other personal identifiable data. The subject's initials, date of birth and trial identification number, will be used for identification. Subjects will be assigned a trial identification number upon enrolment into the study. The study site will maintain a master subject identification Log. If national authorities require specific information to be included in the local/national Informed Consent, then this will be implemented, especially with reference to GDPR. To this end, also the information obtained from the medical staff of the investigational centers will be treated by sponsor and CRO in a confidential manner and only used for the purposes of the study – as is most often already outlined in the specific Investigator Agreements.

5.5.2. Record keeping and archiving

Archiving will be authorised by the Sponsor following submission of the end of study report. Investigators are responsible for the secure archiving of essential trial documents as per their institutional policy. All essential documents will be archived for 5 years after completion of trial. Destruction of essential documents will require authorisation from the Sponsor.

6. STATISTICAL CONSIDERATIONS

An independent statistician will be responsible for all statistical aspects of the investigation.

All statistical analyses will be carried out on the safety population, defined as the subset of randomised patients who receive at least one treatment. No imputation of missing values will be implemented. Only available data will be analysed. In addition, a sensitivity analysis will be carried out to check the main safety results using SAE-data of all evaluable patients, defined as all those patients who received standard of care or those who received the correct dialysis treatment cycle.

Due to the nature of the study all statistical analyses will be descriptive. The categorical variables will be summarised by means of the count and percentages corresponding to each variable category, while continuous variable will be summarised by the mean and Standard Deviation of each distribution or the median and min-max values in case of those variables non-normally distributed.

Clinical Investigation Plan CIP YAQ-002 Version: 7.0 10 October 20	19
--	----

For each treatment arm, treatment-emergent AEs, SAEs, SADEs, ADEs, USADEs and DDs will be summarised by organ system and treatment causality. The number and percentage of patients discontinuing the study due to AEs, SAEs, SADEs or other stopping criteria confirmed by the DSMB (withdrawal of patient consent; development of septic shock; progression to ACLF Grade 3b or more; disseminated Intravascular coagulation; unanticipated serious adverse device effects, device deficiencies, or in the opinion of the PI, the treatment is unsafe to continue) will be summarised by treatment arm.

Secondary and exploratory parameters (changes from baseline at each study visit) will be descriptively analysed by treatment arm by means of the appropriate statistics.

Statistical analyses of safety data will be run when each study cohort is completed (minimally one week FU) and the corresponding results will be communicated to the DSMB.

Special interim data extraction required to comply with the EU ALIVER program.

Access to the ALIVER safety clinical trial data by IBM, one of the Partners of the ALIVER-Consortium, is required to determine if the ALIVER dataset has the same variable set of patient characteristics with those which were included in the CANONIC dataset [5]. This availability is critical to ensure compatibility of the predictive models which IBM is building for ALIVER with the safety clinical trial as input data. Also critical, is an assessment and subsequent potential adjustment of the model to allow for inconsistencies between the CANONIC and the safety clinical trial data e.g. specifications for names, types, and codes of patient characteristics. Access to the clinical data is required at regular interim time points to implement this in two main steps. Initially a process will be executed to filter out patient characteristics that are not considered critically useful in the prediction of mortality rates of ACLF patients. The filtering will be carried out applying statistical criteria using a multivariate feature selection analysis based on the Mutual Information. The filtering will also be carried out using criteria provided by clinicians to determine the usefulness of patient characteristics gathered using exploratory and non-exploratory based laboratory approaches. The second step will be to manage any missing values that could be absent from the safety clinical data provided by considering statistical information extracted from the variables available in the data. If the performance of the CANONIC predictive machine learning models decreases significantly when tested, using the safety clinical data provided, then alternative analytics approaches will be considered and determined.

The techniques which are envisaged for application tor the ALIVER safety data are:

- Standard descriptive statistics to determine the overall structure of the data.
- Data missing values replacement statistical approach.
- Filtering/Selection of groups of patient characteristics according to previously stated usefulness analyses.
- Machine Learning models such as Logistic Regression, XGBoost and, for future work, Deep Neural Networks.

The results obtained from this research work will be made available in a report form not before the clinical trial is completed to guarantee confidentiality and to avoid any bias. No study end-points are assessed by this activity.

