Exploratory end	Objectives	Outcomes Measures
points	To study other exploratory biological and clinical effects of the DIALIVE in patients with ACLF compared with the Standard of Care group. Some of these parameters are centre-specific in line with local expertise, research interest and the capacity to perform these tests.	 Drgan Function and Biomarkers Liver: Changes in MELD score, plasma/serum cCK18/M30 and flCK18/M65 (markers of liver cell death). Kidney: Changes in serum creatinine and urinary NGAL (marker of kidney injury). Brain: West Haven Criteria to assess changes in severity of hepatic encephalopathy. Immune function: Incidence of Infection. Changes in white cell count, and assessment of neutrophil and monocyte function. Assessment of Coagulation and haemostasis: Incidence of thrombotic or bleeding complications, assessment of pro- and anticoagulant clotting factors and complement activation.

Screening/ Baseline	Screening assessments will commence following informed consent. See schedule of
Assessments	assessments.
Additional Study	The treatment phase will occur within the window period of 10 days to achieve one
Assessments	successful treatment cycle with DIALIVE.
(per schedule of	See schedule of assessments.
events)	

Clinical Investigation Plan CIP YAQ-002 Version: 7.0 10 October 2019
--

Sample size/Statistical Analysis

30 evaluable subjects will be randomized to receive either standard of care (SOC) or treatment with DIALIVE (1:1 randomisation).

All statistical analyses will be carried out on the safety population, defined as the subset of randomized patients who receive at least one treatment⁵. No imputation of missing values will be implemented. Only available data will be analysed. In addition, a sensitivity analysis will be carried out to check the main safety results using SAE-data of all evaluable patients

No statistical tests will be performed. All final statistical analyses will be descriptive. The categorical variables will be summarised by means of the count and percentages corresponding to each variable category, while continuous variable will be summarized by the mean and Standard Deviation of each distribution or the median and min-max values in case of those variables non-normally distributed.

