For each treatment arm, treatment-emergent AE's, SAEs, SADEs, ADEs, USADEs and DDs will be summarised by organ system and treatment causality. The number and percentage of patients discontinuing the study due to Aes, SAEs, SADEs or other stopping criteria confirmed by the Data Safety Monitoring Board (DSMB) will be summarized for each arm. Secondary and exploratory parameters (changes from baseline at each study visit) will be descriptively analysed by treatment arm by means of the appropriate statistics.

Statistical analyses of safety data will be run when each study cohort is completed and the corresponding results will be communicated to the DSMB. Data extraction at interim time points do not serve study analyses.

Number of Visits

Patients will undergo the following

Screening assessment (up to 72hrs)6

Study Day 0-randomisation (DIALIVE treatment may commence on this day if all day 1

parameters have been met) Study Day 1 assessments7

Study Days 1-10 treatment phase commences and completes

Study Day 5 assessments

Study Day 10 assessments

Study Day 14 assessments

Study Day 28 assessments

Study Day 90 assessments

One treatment will be defined as any duration of exposure to the DIALIVE.

Viral serology results from up to 8 weeks before the screening period will be accepted

⁶ Screening period (post consent) has been set up to 72 hours to allow sufficient time to gather all relevant clinical information for the subject to be eligible to progress to randomisation. However, if this information becomes available sooner, then randomisation can proceed after that time (without having to wait for 72 hours). For further clarity, the plan for gathering the most recent and relevant clinical information, yet not delaying the start of the study is as follows:

a. Thorough clinical examination of the patient and assessment of FBC, U&E, LFT, Coagulation must be repeated during this period. If randomised to the DIALIVE arm FBC, U&E, LFT, Coagulation results from the screening period may be used if performed up to 24 hours prior to starting treatment unless patients' clinical status has changed.

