The Hepalbin[™]-Adsorbent is a nano-structured carbon filter that removes up to 95% of the industrial stabilisers octonoic acid (caprylate) and N-acetyltryptophanate from commercially available pharmaceutical albumin preparations. These stabilisers are associated with the binding sites of albumin, thus reducing albumin functionality and binding capacity. While in healthy individuals, these stabilisers are metabolized by the liver and have a very short half-life, this is significantly prolonged in liver disease potentially causing accumulation of these materials. The use of Hepalbin[™]-Adsorbent for albumin transfusion indicated that there may be clinical benefit to stabilizer removal in patients with decompensated liver disease in a small controlled study [16].

-

SepteX and oXiris filters are the brandnames of the filters and have no further model specification.

⁸ In the majority of hospitals most recent versions of both Prismaflex and software are available. In Austria the Model ref: 60 23014700 can be in used in Graz; the software version installed is version 8.1

Clinical Investigation Plan	CIP YAQ-002	Version: 7.0 10 October 2019
-----------------------------	-------------	------------------------------

2.2 Definitions.

Screen failures:

- The patient does not meet one or more criteria, which are assessed after the patient (and/or consultee if applicable) signed the Informed Consent; patient can re-enter the study later if at that moment all inclusion criteria and no exclusion criteria are met. Patient informed consent remains valid until end of the study or until withdrawal from the study.
- 2. Patient who did not start dialysis before the end of DAY 1 if randomized to the DIALIVE treatment arm, is considered a screen failure; such a patient does not have to resign a consent form, but can re-enter the study via de novo demonstration of compliance with the in- and exclusion criteria.

Patient withdrawal: a patient (or the consultee if applicable) can withdraw consent at any time. No further clinical data can be collected as of that moment; the data collected prior to that moment, remain part of the clinical study.

Patient exclusion: a patient is considered excluded from the study (and from re-entering into the study):

- 1. Upon demonstration of more than 2 interuptions of more than 24 hrs between subsequent dialysis sessions and within the first 10 day time period after randomization (DIALIVE arm);

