Patients presenting with, or developing during the study period, severe actue renal failure requiring renal support, will receive continuous renal replacement therapy (CRRT) as per standard local practices. This would apply to subjects in both SOC and DIALIVE arms. For those in the DIALIVE arm, the same vascular catheter which is used for DIALIVE treatment may be used for CRRT following the completion of the DIALIVE treatment session. It is however envisaged

that increased intensity of dialysis component in the DIALIVE system (from 1lit/hr to 1.5lit/hr) and allowance for fluid removal in the new protocol may delay or remove altogether the need for CRRTin these situations. The decision for additional CRRT would depend on clinical situation and will be taken by the site PI.

DIALIVE arm consists of standard of care (defined above), plus DIALIVE treatment.

A DIALIVE treatment session denotes treatment for the day, whereas A DIALIVE treatment cycle refers to the total number of treatment days.

A DIALIVE treatment **session** = A minimum, cumulative duration of 8 to 10 hrs (± 30 min) of the DIALIVE treatment, thus allowing for breaks which may be planned (for example patients needing to go for imaging) or unplanned (device clotting, issues with vascular access or other any other unplanned reasons). A break within a treatment session (consisting of a cumulative time longer than 4hrs), or a cumulative duration of less than 8 hrs of dialysis during one day constitutes a session failure for that day. A session failure will require to restart the dialysis session within 24 hrs after the end of the previous session and will reset the start of the dialysis cycle.

A DIALIVE treatment **cycle**= Consists of 3 consecutive days of 8-10 hrs of DIALIVE treatment sessions on each day within the 10 day window period. A break of more than 24hrs between each treatment session will require a new baseline (i.e. a new treatment cycle commenced). A second failed treatment session within the 10 day window period would result in patient exlusion. The patient must have completed one successful treatment cycle within the 10 day window period to be considered evaluable.

Day of randomization constitutes study Day 0.

The first treatment session (DIALIVE arm only) must commence before the end of study Day 1. As such, dialysis might also start on the day of randomization which might created confusion as 'the first day of dialysis' then concurs with DAY 0 of the study schedule.

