Commencement of DIALIVE treatment session i.e. connection of patient to the Prismaflex machine = time point 0, can occur at any time before the end of study Day 1 subject to availability of all relevant information required for treatment to commence. All blood samples should be measured from this time point. Any pre samples required should be taken just before connection.

Nuts and bolts of DIALIVE Treatment: a ready reference

-Before starting treatment

The patient to be moved to an intensive care unit or similar once randomised to DIALIVE. Appropriate monitoring needs to be instituted including the following:

- Insertion of an arterial line for continuous invasive blood pressure monitoring and blood sampling
- Insertion of a vascular catheter for DIALIVE treatment
- Insertion of a central venous catheter for prompt treatment with vasopressors if required (Lines should be inserted under USS guidance. Correction of clotting abnormalities, if any, should follow local protocols. The line positions should be confirmed through appropriate means; e.g. CXR for neck lines).

 * NB: Majority of ACLF grade 3 patients are likely to be already in the ICU with the above monitoring in situ.

Additional tests (Baseline samples for FBC, U/E, LFT, coagulation, septic screen will already have been collected to check eligibility) prior to commencing DIALIVE therapy will be done:

Arterial blood gas analysis

- Haemolysis screen (FBC including reticulocyte count, blood film, unconjugated and conjugated bilirubin, LDH, haptoglobin, urinary free haemoglobin) – to be performed only on D1, before and after therapy
- DIC screen, if clinically indicated
- And, Endotoxin Activity Assay (EAA) analysis (start of day 1, 2 and 3)
- Blood to be collected as part of biobank samples.(start of day 1, 2 and 3)

Fluid pre-loading of up to 500mls over 1-2 hours is implemented, the volume and speed of fluid therapy to be determined on a clinical basis, and the choice of fluid would preferably be albumin (4.5 or 5% solution as per local availability).

- during dialysis session

- Anticoagulation with unfractionated heparin and/or prostacycline analogues (the dose as per local protocols)
- Blood flow rates on DIALIVE device to be started at 50 mls/min and increased gradually over 1-2 hours to up
 to a maximum of 250 mls/min

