	complete by clamping off oXiris® dialysing fluid-effluent circuit
	Operation
	Prismaflex control, monitoring and safety features all engaged
	 CVVHDF proceeds as indicated except blood path series connection of septeX[™] and oXiris®
	ICU/HD monitoring per CIP and institutional standard of care
	Restitution of all extracorporeal blood during

Clinical Investigation Plan

CIP YAQ-002

Version: 7.0 10 October 2019

	Clinical Investigation Plan	CIP YAQ-002		Version: 7.0 10 October 2019
				 
				d at end of session, except in case of filter thing.
Circumventing of Prismaflex monitoring and control features:		Function	onal compatibility of Prismaflex, septeX™	
-	LDD adverse events		set + o	(iris® set verified in porcine model
- exanguination - thromboembolism		Prisma	iflex pre-programmed sequential	

clotting exacerbation of symptoms and complications of liver failure

death

mistakes Prismaflex control, monitoring and safety features

procedures mostly eliminate slips, lapses and

Prismaflex CE marked for CVVHDF

engaged

Investigator familiarity with CVVHDF

Use is restricted to qualified investigator and supervised qualified support familiar with aseptic technique and liver failure patients

Blood loss due to venous cannulation

- Undertaken by experienced staff trained in the procedure
- Standard clinical procedures are followed
- Coagulation results reviewed prior to cannulation
- CIP specifies ICU/HDU monitoring particularly monitoring:
 - liver function
 - cardiovascular function
 - renal function

Hypotension induced by DIALIVE, especially in patients who may be intravascularly depleted because of fluid restriction, diuretic therapy, inadequate oral intake and anemia, or those with evidence of vasoplegia.

- perform fluid preloading
- simultaneous replacement of lost albumin
- stepwise increase of blood flow rate through the **DIALIVE**
- stepwise increase of replacement fluid
- closely monitor the patient

3.3 Residual risks associated with participation in the clinical investigation.

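### The main SAE set is defined by DIALIVE exposure, so a patient randomised to DIALIVE but not dialysed by the end of Day 1 falls outside both planned SAE analyses

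*Protocol*

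**What the plan says.** The synopsis states: "All statistical analyses will be carried out on the safety population, defined as the subset of randomized patients who receive at least one treatment". Section 6 repeats the definition: "defined as the subset of randomised patients who receive at least one treatment". A footnote in the synopsis, the only place where one treatment is defined, equates it with any "duration of exposure to the DIALIVE"; it does not mention SOC.

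Section 6 adds a sensitivity analysis of SAEs in evaluable patients: those who received SOC, or who received the correct dialysis cycle. For the DIALIVE arm, Section 2.2 says: "The patient must have completed one successful treatment cycle within the 10 day window period to be considered evaluable".

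On patients who are randomised but never connected, Section 2.2 says: "Patient who did not start dialysis before the end of DAY 1 if randomized to the DIALIVE treatment arm, is considered a screen failure". Section 5.1.7 replaces screen failures. Section 5.3.4 places enrolment at randomisation (Day 0). Section 2.2 keeps screen failures in follow-up for at least 28 days, and Section 12.5 records adverse events from consent.

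The primary endpoint (Section 5.1.2) is the percentage of subjects with an SAE from Day 1 to Day 10, with emphasis on how the two groups compare.

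**The concern.** Randomisation was adopted, according to Section 4.2, to give unbiased and balanced data on the two arms. A filter that is applied after randomisation and can remove patients from one arm only works against that aim. If the footnote is read so that SOC counts as treatment, every SOC patient qualifies, and the filter bites only on DIALIVE patients who are not connected.

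The interval it removes is not free of risk. Section 2.2 says: "The patient to be moved to an intensive care unit or similar once randomised to DIALIVE". The preparation before connection includes an arterial line, a central venous line and "Insertion of a vascular catheter for DIALIVE treatment". Section 3.2 lists "Blood loss due to venous cannulation" among the risks. An SAE from these steps in a patient who never starts dialysis would count in neither planned SAE percentage.

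At stake is the between-arm SAE percentage. It is the primary endpoint, and Section 5.3.7 says that the DSMB decides on continuation by comparing adverse events between arms in each cohort.

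**Working it through.** **Check of the stated numbers.** 5 cohorts × 6 = 30 evaluable patients, 15 per arm, as stated. Section 5.1.7 anticipates 17% dropout from the first two cohorts. The derivation is not given, but 2/12 = 16.7% fits it.

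**One patient traced through the rules** (randomised to DIALIVE, not dialysed by the end of Day 1):

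- Enrolled: yes (5.3.4).
- Label: screen failure (2.2); replaced (5.1.7).
- Safety set: out, because there is no exposure (synopsis footnote, Section 6).
- Evaluable set: out, because there is no completed cycle (2.2, Section 6).
- Data: collected for at least 28 days (2.2), but assigned to no analysis set.

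**Effect on the DIALIVE percentage.** Let N be the treated DIALIVE patients, k the non-starters, p the SAE risk over all N + k allocated, and s the risk in non-starters.

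- Observed risk = [p(N + k) − s·k] / N.
- Shift = observed − p = (k/N)(p − s).

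Inputs for N: 15 (evaluable target); 15/(1 − 0.17) ≈ 18 (17% dropout); 15 × 8/6 = 20 (Appendix 7 reports 8 DIALIVE patients enrolled for 6 evaluable). The documents give neither p nor s. I assume p = 0.3 to 0.7 and s = 0 to 1, so the largest |p − s| is 0.7.

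| Non-starters | N = 15 | N = 18 | N = 20 |
|---|---|---|---|
| 0 | 0 | 0 | 0 |
| 1 | ±4.7 points | ±3.9 | ±3.5 |
| 2 | ±9.3 | ±7.8 | ±7.0 |

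These are maxima. If s = p, the shift is 0. If non-starters have more SAEs than the rest (s > p), leaving them out flatters the device; if fewer, it counts against the device.

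Cross-check with counts: if 6 of 15 dialysed patients have an SAE (40.0%), adding one non-starter with an SAE gives 7/16 = 43.75%. The formula gives (1/15)(0.4375 − 1) = −3.75 points, which agrees.

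**Sensitivity set.** It drops DIALIVE patients without a correct cycle and no SOC recipient. Appendix 7 reports 2 of 8 DIALIVE patients in cohorts 1-2 as non-evaluable for not completing the minimum treatment. It also reports two DIALIVE deaths within 24-36 hours of starting treatment. A patient dead by then could not complete the present three-day cycle, so the two pairs are probably the same patients. If so, DIALIVE deaths go from 2 of 8 in the main set to 0 of 6 in the sensitivity set.

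**The case against.** **No non-starter is on record.** Appendix 7 accounts for all 8 DIALIVE patients as 6 evaluable and 2 who did not complete the minimum treatment. This stands: the recorded effect on the main set is 0, and the point sizes above rest on assumed risks.

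**SOC exclusion is only a literal reading.** Section 6 summarises each arm and names SOC recipients in its evaluable set, so no analyst would empty the SOC arm. This also stands, but the sensible reading leaves a filter on one arm.

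**A non-starter did receive SOC,** since the DIALIVE arm includes it, and might count as evaluable. That reading would also make every patient with an incomplete cycle evaluable, against Sections 2.2 and 5.1.7.

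**The SAE would be seen anyway.** Every SAE is reported in detail (5.1.5), the DSMB reviews all safety data (12.3.3), and the UK authority receives three-monthly SAE percentages of all enrolled participants (Appendix 6). So nothing is hidden. But a listing, or a percentage not split by arm, does not put the patient into the between-arm endpoint. Events on Day 0 lie outside the Day 1-10 window whichever set is used.

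**A completers set is conventional beside an exposed set.** Agreed. The sensitivity analysis is not wrong in itself; what is missing is sight of the patients it leaves out.

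**Stronger readings that the documents do not support:**

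- A reader might infer that the two early deaths vanish from the main analysis. Both patients had started treatment, so both stay in.
- A reader might take it as proven that they are the two non-evaluable patients. Appendix 9 shows that the cycle was changed to three sessions in version 6.0, and the rule in force for cohorts 1-2 is not shown.
- A reader might infer that the sensitivity set takes the percentage with any SAE in cohorts 1-2 from 25% to 0%. That requires no other DIALIVE patient to have had an SAE. It fits poorly with the observed events in Section 12.5 and with the two device-related SAEs in one subject recorded in Appendix 9.
- A reader might infer that SOC deaths within 10 days are deleted because Section 5.1.7 makes them replaceable. Section 6 counts all SOC recipients as evaluable. How these deaths, and re-entered patients, are tabulated is largely a matter for the SAP, which is not shown.

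**Conclusion.** The point holds as a flaw in the protocol's own definitions, and it should be fixed. The main set rests on a definition of treatment that names only DIALIVE, and an enrolled patient who is not dialysed by the end of Day 1 belongs to neither SAE set. The consequence is conditional: 0 points if no such patient occurs, and at most about 3.5 to 4.7 points per non-starter in either direction, assuming an SAE risk of 30-70% overall and 0-100% in non-starters, with 20 to 15 treated. The documents do not show that it has favoured the device.

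The one-sided loss from the sensitivity set is documented for cohorts 1-2 (2 of 8 DIALIVE patients). That these are the early deaths is probable but not proven, and the main set keeps both deaths. The study is descriptive, with no hypothesis test and an arbitrary sample size, so no error rate or power is affected.

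**What to change.** - State in the synopsis and Section 6 that the safety population is all SOC patients plus all DIALIVE patients with any exposure.
- Add a descriptive Day 1-10 SAE summary of all randomised patients by allocated arm, including Day 1 non-starters, in the final report and in each DSMB review.
- In the analysis, use the screen-failure label only before randomisation, and align Sections 2.2 and 5.1.7 with enrolment at randomisation in Section 5.3.4. The rule on when dialysis must start need not change for this.
- Beside the evaluable-set analysis, list the DIALIVE patients it leaves out, with their SAEs.

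The cost is wording in four places, one table per review and one listing. No new data are needed, because adverse events are recorded from consent and screen failures are followed for at least 28 days. The drawback is that undialysed patients slightly dilute the DIALIVE arm in the added table, so the exposed set should stay alongside it for device-related harm.
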